9.0 OTHER INSTITUTIONS

If a part of the study is conducted by an institution that has not previously been identified within the Investigational plan each institution's contact information will be documented below;

No other institutions will be part of this study.

10.0 ADDITIONAL RECORDS AND REPORTS

If this is an IDE study, additional records and reports will be maintained on the investigation in addition to those prescribed in 21 CFR 812 sub-part G. If this is a non-IDE study, the study summary will be maintained on the investigation and may include those prescribed in 21 CFR 812 sub-part G.

Additional Records and Reports:

Report	Submit To	Description/Constraints
N/A	N/A	This is a non-IDE study; no additional records or reports will be maintained.

A description of this clinical trial will be available on http://www.ClinicalTrials.gov, as required by U.S. Law in accordance with the Final Rule for Clinical Trials Registration and Results Information Submission (42 CFR Part 11). The sponsor will be responsible for the submission and maintenance of http://www.ClinicalTrials.gov records. The Principle Investigator will be responsible for providing accurate data in a timely manner for compliance.

11.0 PREGNANCY

Females may not participate in this study if they are pregnant, breastfeeding, were pregnant within the last three months or are planning a pregnancy during the study.

If the subject thinks they have become pregnant during the study, it is important that they inform the Investigator immediately. If she becomes pregnant or thinks that she may be pregnant, she will be removed from the study and will be asked to perform a final evaluation similar to the final follow-up visit. The Investigator may request to track the pregnancy and will report the pregnancy to the Sponsor.

12.0 SUBJECT WITHDRAWAL

The subject is free to withdraw from this study at any time. The subject must inform the Investigator immediately if they intend to withdraw. To terminate the subject's participation in this study, they must contact the Investigator at the contact information listed on page one of the informed consent form. They will be asked to come to the study clinic or Investigators office to complete a final follow up visit and may be asked to perform end of study procedures. Their decision to participate in this study or to withdraw from this study will not influence the availability of their future medical care and will involve no penalty or loss of benefits to which they are otherwise entitled.

The Investigator in charge of the study can remove the subject from this study without their consent for any reason, including, but not limited to:

- a) His/her judgment that any condition or circumstance may jeopardize their welfare or the integrity of the study.
- b) Their failure to follow the instructions of the Investigator(s).
- c) If the study is stopped by the sponsor and/or Investigators participating in the study prior to completion.

Data collected prior to withdrawal will be used in data analysis but after withdrawal no further data will be collected.

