2.14 Adverse Event Recording

All data captured must be supported by the Investigator's timely assessment and documentation of the adverse event in the case report forms or source documents. All documented adverse events will be reviewed by the Sponsor or designee to determine whether the adverse event meets regulatory reporting requirements and to ensure timely adverse event reporting to meet local and global regulatory requirements. All adverse events must be followed until their resolution.

Adverse Events Pertaining to the Elite iQ Device:

- Subjects may experience some temporary erythema, edema, bruising, or irritation of the skin around the treatment site.
- Scarring, though rare, can occur following any laser procedure.
- Blistering during treatment may be an indication of sun exposure or an excessive fluence setting for the skin type. Blistering can occur during the first three days following the laser procedure.
- Other acute changes may include scaling or scabbing. These changes are often associated with higher energies and their incidence decrease when treatment energies are reduced.
- Histamine/Hives: some subjects may develop raised papules similar to hives. This irritation usually subsides in a few hours.
- Pustules, pimples, or folliculitis may develop in the first few days following treatment.
- Hyperpigmentation or hypopigmentation can occur following the laser treatment. Pigmentary changes have been reported to be transient although they may last for several months or longer.
- Hemosiderin Staining- The treated vessel may leak tiny amounts blood into the tissue. When the red blood cells die, iron released from the hemoglobin is converted into hemosiderin and stored in the tissue beneath the skin. This shows up as a brown/purple stain on the skin. It usually will fade over time, but some may require further treatment to resolve.

Adverse Events Pertaining to Gel:

The gel is a water-based gel that may be placed on the skin during the Elite iQ treatment. No known adverse events are documented. However, an allergic reaction is always possible when placing a topical gel onto the skin. Allergic reaction may include a mild reaction such as skin redness, irritation or hives.

Adverse Events Pertaining to Anesthesia:

Topical anesthesia, such as but not limited to; EMLA, LMX and Lidocaine/Tetracaine, will be used. The most common side effects for most anesthetics include redness, blanching, swelling and application site reaction.

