2.15.3 Patient Populations

Interim results may be collected and reported. All data will be analyzed at the end of the study. The primary analysis will be performed by the intention-to-treat approach. Everyone who begins the treatment is part of the study whether he or she completes the study or not. Additional perprotocol analysis may also be performed on subjects who complete the entire clinical trial according to the protocol. The most appropriate method of handling missing values will be chosen based on the individual trial goals, endpoints and context.

The analysis of demographic, medical history, and efficacy variables will be based on all patients who are randomized and receive at least one treatment. The analysis of safety data will be based on all patients who are randomized, receive at least one treatment, and have at least some safety data.

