2.15.5 Analysis of Efficacy Variables

The primary efficacy variable is the change from baseline to visit 7 (60 days post last treatment, +/- 30 days) with respect to the indication being treated as evaluated by physician grading with CGAIS. Baseline is defined as the last assessment prior to the first treatment. The change from baseline to visit 13 will be analyzed using a Mixed Model Repeated Measures Analysis of Variance. A pairwise treatment group comparison at visit 7 will be performed using the results of this analysis. If a patient has no post-baseline assessment of the primary efficacy variable the patient data will be excluded from the statistical analysis of the improvement. Statistical

significance with respect to the treatment group comparison at visit 7 will be declared if the two-sided p-value is < 0.05. For each treatment group summaries will be prepared for both the observed assessment and the change from baseline. Subject satisfaction results from Visits 12 and 13 will also be included in the summary. The summaries will include the sample size, mean, median, standard deviation, minimum, and maximum. Categorical variables will also include a summary which will include the number and percent of patients for each outcome. The statistical significance of the mean change from baseline for each treatment group will be determined using a student's paired t-test.

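### Section 12.0 ends data collection at withdrawal, which conflicts with the adverse-event follow-up rules and the pregnancy exit evaluation and can drop early leavers from the intention-to-treat efficacy analysis

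*Combined protocol and SAP*

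**What the plan says.** Section 12.0 covers two ways of leaving. For a subject who chooses to withdraw: "They will be asked to come to the study clinic or Investigators office to complete a final follow up visit", with end-of-study procedures possible. Separately, the Investigator "can remove the subject from this study without their consent for any reason"; the listed reasons include danger to the subject's welfare, failure to follow instructions and stopping of the study. That paragraph requests no exit visit. The section then closes, for both routes: "Data collected prior to withdrawal will be used in data analysis but after withdrawal no further data will be collected".

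Other sections bear on the same subjects:

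- Section 11.0, on pregnancy, known or suspected: "she will be removed from the study and will be asked to perform a final evaluation similar to the final follow-up visit". Tracking of the pregnancy is also allowed.
- Section 2.14: "All adverse events must be followed until their resolution". Section 14.0 ends follow-up at resolution, stabilization, another explanation or loss to follow-up. Withdrawal is not in that list.
- Section 2.15.3 names intention-to-treat as the primary approach: "Everyone who begins the treatment is part of the study whether he or she completes the study or not". It leaves the missing-data method to be chosen later.
- Section 2.15.5: "The primary efficacy variable is the change from baseline to visit 7", graded with the CGAIS. It adds: "If a patient has no post-baseline assessment of the primary efficacy variable the patient data will be excluded from the statistical analysis". The schedule in 2.12 marks the Investigator Questionnaire at Visit 7 only.

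**The concern.** A site cannot obey both sets of rules for a subject who leaves with an open adverse event: 2.14 and 14.0 require follow-up and 12.0 forbids it. This matters because safety is a primary objective (1.2), and 2.15.1 makes an acceptable side-effect profile part of overall success. Section 2.14 itself warns that pigmentary changes may last for months and that some hemosiderin staining may need further treatment, so an event can easily outlast a subject's exit.

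On efficacy, the CGAIS has one scheduled time point. If nothing is collected at exit, an early leaver has no grade and drops out of an analysis described as counting everyone who began treatment. If leaving is related to a poor result, the observed response is too high. With 20 subjects planned, each one is 1/20 = 5 percentage points.

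**Working it through.** **Texts side by side**

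| Situation | Section 12.0, last sentence | Other rule | Compatible? |
|---|---|---|---|
| Subject chooses to withdraw, attends exit visit | No data after withdrawal | 12.0: final visit requested | Yes, if the visit precedes withdrawal; the text does not say |
| Adverse event still open after that visit | No data | 2.14, 14.0: follow it | No |
| Removed by the Investigator | No data; no visit requested | 2.14, 14.0: follow open events | No |
| Removed for pregnancy | No data | 11.0: evaluation follows removal | No |
| Leaves before Visit 7, no exit CGAIS | No data | 2.15.3 counts the subject; 2.15.5 excludes the subject | No |

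**What safety keeps.** Data from before withdrawal are used (12.0). The safety set needs one treatment and some safety data (2.15.3), and pain and adverse events are recorded at treatment visits (2.12). The loss is confined to events that start, or whose outcome becomes known, after exit.

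**Scale for efficacy (illustration).** The 20 subjects in 2.15.2 include departures, but no dropout rate, effect size or power is given, so there is no planned figure to reproduce. Inputs from the plan are N = 20 and the secondary criterion in 2.15.1: statistical significance or at least 80% response, with no denominator stated. The number of withdrawals d is assumed.

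With withdrawals left out, n = 20 − d and the criterion needs r = 0.8n responders, rounded up:

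- d = 0: 16/20 = 80%.
- d = 2: 0.8 × 18 = 14.4, so 15; 15/18 = 83%, against 15/20 = 75% of all treated.
- d = 4: 0.8 × 16 = 12.8, so 13; 13/16 = 81%, against 13/20 = 65%.

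Now assume a true response of 70% among all 20. If every withdrawal is a non-responder (the worst case), the rate among those remaining is 14/n. If withdrawal is unrelated to outcome, it stays at 0.70. The chance of reaching 80% is the binomial tail P(X ≥ r) with n subjects. In the last column the rate is again 14/n, but withdrawals count as non-responders, so 16 of 20 are needed.

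| d | Worst case, excluded | Unrelated, excluded | Worst case, counted as non-responders |
|---|---|---|---|
| 0 | 0.24 | 0.24 | 0.24 |
| 2 | 0.41 | 0.17 | 0.20 |
| 4 | 0.87 | 0.25 | 0.12 |

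For unrelated withdrawal the chance stays between 0.13 and 0.30 over d = 1 to 5. It moves because n is smaller and r is rounded, not because the response rate is biased.

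**The other route to success.** Section 2.15.1 also accepts a significant difference from a mean score of 4. Suppose response means a CGAIS of 3 or better (the plan does not define it) and every responder scores 3.

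- 15 of 20 respond, five score 4: mean 3.25, SD 0.44, t = −0.75/(0.44/√20) ≈ −7.5, p < 0.001.
- 15 of 20 respond, five score 5: mean 3.50, SD 0.89, t ≈ −2.5, p ≈ 0.02.
- 13 of 20 respond, seven score 4: mean 3.35, SD 0.49, t ≈ −5.9, p < 0.001.
- 13 of 20 respond, seven score 5: mean 3.70, SD 0.98, t ≈ −1.4, p ≈ 0.19.

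So at 75% response the criterion would be met by significance in both examples. At 65% it depends on how poor the remaining scores are.

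**The case against.** The strongest reply is that 12.0 addresses a subject who intends to withdraw, asks for a final visit, and only then closes data collection. In that order the visit completes the exit and its data count. This is a fair reading and it rescues subject-initiated withdrawal. It does not reach the Investigator-removal paragraph, where no visit is requested, nor 11.0, where removal comes first, nor events that outlast the visit.

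A second reply is that stopping data collection once consent is withdrawn is proper. That stands. The gap is that 12.0 does not separate stopping treatment, removal by the Investigator and withdrawal of consent to further data. The consent form was not available for this review and may already do so.

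A third is that the exclusion in 2.15.5 and the open missing-data method in 2.15.3 would drop any subject without a grade, whatever 12.0 says. That is correct, so rewording 12.0 alone would not be enough.

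A reader might also infer that both primary objectives lose the subjects who did worst and so look better than the truth. The documents do not support that. Withdrawn subjects stay in the safety set with their earlier data. The primary efficacy objective in 1.2 is blinded photography, and 2.13 has photographs taken at all visits, so an early leaver may have later images. The CGAIS is called primary in 2.15.5, but 1.2 lists Investigator questionnaires as secondary. The reasons for withdrawal are unknown.

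**Conclusion.** The conflict between 12.0 and sections 2.14, 14.0 and 11.0 is in the current text and should be resolved. For safety, the exposure is limited to onset and outcome of events after exit. For efficacy, a subject who leaves before Visit 7 without an exit assessment is excluded under 2.15.5, which departs from the plan's own intention-to-treat definition.

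The size is conditional. An upward bias needs withdrawal to be related to outcome, which is plausible but undocumented. With two non-responders leaving, the shift is 83% against 75%. It concerns a secondary criterion that can also be met by significance, so the formal conclusion may not change. The effect on the overall result is further limited because this is an open-label study of up to 20 subjects whose success rule is largely qualitative. The change is nevertheless worth making, since it costs little and protects data that the plan already asks for.

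**What to change.** Replace the last sentence of 12.0 so that it agrees with 2.14, 11.0 and 14.0:

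1. Stopping treatment, or removal by the Investigator, does not by itself end data collection.
2. Unless the subject withdraws consent to further data collection, the final visit (photographs, CGAIS, questionnaires, adverse events) is requested for every withdrawn or removed subject, and its data are analysed.
3. Open adverse events are followed as 2.14 and 14.0 already require.
4. The case report form records stopping of treatment, Investigator removal and withdrawal of consent as separate items.

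In 2.15.5, report how many treated subjects have no post-baseline CGAIS. Give the response rate with all treated subjects in the denominator, counting those subjects as non-responders, beside the observed-case rate. This covers anyone who declines the final visit.

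The cost is a few sentences, a check that the consent form matches, and exit visits for Investigator-removed subjects, for whom 12.0 requests none at present. The reported response rate may be less favourable.

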13.0 PHOTOGRAPHY

Standardized photographs will be taken of the treatment area. The subject will be asked to remove jewelry, make-up, and lotions prior to each photo session. Photographs will be taken with an appropriate high-resolution digital camera. Camera settings (lighting, distance, background, polarization, etc.) will be reproduced at each visit, so that photographs are suitable for comparison. Photographs will be taken of the treatment area for study purposes. If the subject does not wish to have their photographs taken, they cannot be in the study.

14.0 ADVERSE REACTIONS DEFINITIONS AND REPORTING REQUIREMENTS

All adverse events that occur, starting from the time of the first treatment, will be recorded in the source documents and Case Report Forms (CRF).

Adverse Events (AE) occurring will be captured and followed until the condition resolves, stabilizes, is otherwise explained, or the subject is lost to follow-up. Subjects will be instructed that they may contact the Investigator at any time throughout the course of the study.

The Investigator and/or designated study staff will review each event and assess its relationship to the study device (not related, unlikely, possible, probable, and highly probable). The following definitions will be used for rating relationship to the Elite iQ treatments:

- Not related The event is clearly related to other factors such as the subject's clinical state, therapeutic interventions, or concomitant medications administered to the subject.
- Unlikely The event was most likely produced by other factors such as the subject's clinical state, therapeutic interventions, or a concomitant medication administered to the subject; and does not follow a known response pattern to the investigational product.
- Possible The event follows a reasonable temporal sequence from the time of investigational product administration; **and/or** follows a known response pattern to the study sampling sessions; **but** could have been produced by other factors such as the subject's clinical state, therapeutic interventions, or concomitant medications administered to the subject.
- Probable The event follows a reasonable temporal sequence from the time of investigational product administration; **and** follows a known response pattern to the investigational product; **and** cannot be reasonably explained by other factors such as the subject's clinical state, therapeutic interventions, or concomitant medications administered to the subject.

Highly Probable – The event follows a reasonable temporal sequence from the time of investigational product administration; and follows a known response pattern to the investigational product; and cannot be reasonably explained by other factors such as the subject's clinical state, therapeutic interventions, or concomitant medications administered to the subject; and either occurs immediately following investigational product administration, or improves on stopping the investigational product, or reappears on repeat exposure, or there is a positive reaction at the application site.

Each adverse event reported will be graded on a 3-point severity. Using the following definitions for rating severity will be used:

- Mild easily tolerated, causing minimal discomfort, and not interfering with normal everyday activities.
- Moderate sufficiently discomforting and may interfere with normal everyday activities.
- Severe incapacitating and/or preventing normal everyday activities.

A Serious Adverse Event (SAE) is any adverse device experience that results in any of the following outcomes: death, a life-threatening adverse device experience, in-patient hospitalization or prolongation of hospitalization, a persistent or significant disability/incapacity, or a congenital anomaly/birth defect. Important medical events that may or may not result in death, be life-threatening, or require hospitalization may be considered a serious adverse device experience when, based upon appropriate medical judgment, they may jeopardize the subject or subject may require medical or surgical intervention to prevent one of the outcomes listed in this definition

If any of the above adverse events are serious as defined by the FDA Code of Federal Regulations (CFR), Title 21, special procedures will be followed. All serious adverse events will be reported within 24 hours of acknowledgment to the Sponsor whether or not the serious events are deemed sampling session-related. All serious event reporting will adhere to 21 CFR part 812 and the IRB will be notified accordingly.

The SAE information will be entered into the database and a desk copy of the complete SAE report will be submitted to the study file.

Adverse events, whether serious or non-serious, will be followed until the condition is resolved, stabilized, otherwise explained or the subject is lost to follow-up. Adverse events will be captured throughout the study and where appropriate, medical tests and examinations will be performed to document the resolution of event(s). Outcomes may be classified as resolved, improved, unchanged, worse, fatal, unknown or lost to follow-up. Following the resolution of any study-associated adverse events there will be no further adverse event reports for that subject.

Reporting Adverse Events:

Report Submit To Description/Constraints	
--	--

Adverse Events, Unanticipated Adverse Device Effect	IRB and Sponsor	If an unforeseen complication is determined to be an unanticipated adverse device effect, the investigator's report must be submitted within 10 working days after the investigator first learns of the effect.
Serious Adverse Events	IRB and Sponsor	The sponsor must be notified within 24 hours of serious adverse events. The IRB must be notified within 1 working day of serious adverse events as defined by FDA guidelines.

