2.15 Statistical Analysis

2.15.1 Hypothesis

For this study to be considered a success, parameters are developed, and the side effect profile is acceptable to the Physician as it relates to this type of treatment.

For secondary objectives to be considered a success, the results from any assessments will need to be statistically significant or have $\geq 80\%$ response rate. In cases where the subject's improvement is being graded on a scale, such as the GAIS scale, we will test the statistical significance of our results against a hypothetical population that would have no change (average score of 4).

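### The only adverse event severity scale has no criterion for visible skin change or need for corrective treatment, so painless scarring, pigment change or staining will generally default to Mild

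*Combined protocol and SAP*

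**What the plan says.** Section 14.0 makes grading compulsory: "Each adverse event reported will be graded on a 3-point severity". There are three levels:

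- The lowest, Mild, is for an event that is "easily tolerated, causing minimal discomfort, and not interfering with normal everyday activities".
- The middle level, Moderate, is for an event with enough discomfort that daily life may be disturbed.
- The highest, Severe, is for an event that is "incapacitating and/or preventing normal everyday activities".

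The document contains no other severity scale for adverse events.

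Section 2.14 lists the effects expected of the device. On scarring: "Scarring, though rare, can occur following any laser procedure". On hyper- and hypopigmentation: "Pigmentary changes have been reported to be transient although they may last for several months or longer". On hemosiderin staining: "It usually will fade over time, but some may require further treatment to resolve".

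Safety, assessed by collecting side effects, is a primary objective (1.2). Section 2.15.1 makes study success depend in part on whether "the side effect profile is acceptable to the Physician as it relates to this type of treatment", and sets no threshold. Section 2.15.6 plans counts and percentages of patients per outcome for pain and adverse events. It does not say whether adverse events are tabulated by type, severity or persistence.

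**The concern.** In an elective aesthetic procedure, how bad a skin effect is depends largely on how visible it is, how long it lasts and whether it needs treatment. None of the three grades mentions any of these. Read literally, the scale puts a painless scar level with redness that fades in hours, and below brief soreness that disturbs one day's activities.

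Severity is the only ranking the protocol defines for how bad a non-serious event is. If the report, or the physician judging the profile, relies on that ranking, the cosmetic harms named in 2.14 could disappear into a profile that reads as all mild.

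**Working it through.** The point turns on wording, and the plan gives no figure to reproduce. The check sets the scale against the listed harms and then looks at what else records them.

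**Step 1: the scale against the harms.** Take a scar, pigment change or stain that does not hurt and does not limit activity.

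- Severe requires incapacity or prevention of activities. Not met.
- Moderate requires enough discomfort, with possible interference. Not met.
- Mild requires three things together: easy tolerance, minimal discomfort and no interference. The last two are met. The first is met unless the rater decides that a distressing mark is not easily tolerated.

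If the rater does decide that, the event fails Mild and still does not satisfy the literal wording of Moderate. A higher grade then depends on reading cosmetic distress into discomfort, which the text does not address. Since a grade is compulsory, Mild is the usual result, and two raters could grade the same scar differently. This applies to four named effects: scarring, hyperpigmentation, hypopigmentation and hemosiderin staining.

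**Step 2: what else records these events.**

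- Outcome (14.0): categories include improved, unchanged and worse. They describe the course of an event, not its importance: a faint mark and a disfiguring scar can both be unchanged.
- Follow-up of events: 14.0 allows it to end once an event stabilizes, as a permanent scar would; 2.14 says until resolution.
- Photographs (2.9, 2.13, 13.0): taken at follow-up under standardized conditions and used for safety, but with no rule for grading or tabulating what they show.
- Seriousness (14.0): covers disability or incapacity, plus important medical events by medical judgement. Permanent skin damage is not named, so inclusion is discretionary.

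Persistence is therefore recorded, but nothing ensures that it appears in the results.

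**Step 3: could status at Visit 7 set the grade?** Visit 7 falls 30 to 90 days after the last treatment (2.9, 2.12). An area may receive up to five treatments, 2 to 10 weeks apart (2.7).

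- Shortest time from the preceding treatment to Visit 7 (event after the last treatment): 30 days.
- Longest (event after the first of five): (5 − 1) × 10 weeks + 90 days = 280 + 90 = 370 days, and 370 / 7 ≈ 53 weeks.

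Identical events could have 30 days or about 53 weeks to fade. Status at Visit 7 is worth reporting, but it should not decide the grade.

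**Step 4: why an interval is needed.** With 20 subjects (2.15.2), each subject is 1/20 = 5 percentage points. Even if no subject has a lasting change, the exact two-sided 95% upper limit is 1 − 0.025^(1/20) = 1 − 0.832 = 16.8%.

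**The case against.** The strongest reply is that no planned result uses the grade. The objective is to collect side effects, 2.15.6 does not specify a table by severity, and 2.15.1 rests on the physician's overall view with no severity threshold. A scar would be recorded and counted as a scar, followed, given an outcome and photographed. The case report form is not part of the text available, so it may hold further fields. All of this stands. A reader might infer that the primary safety result will understate harm; the documents do not support that as fact.

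It is also fair that Mild is an inference from the wording and that the rater has some room in judging what is easily tolerated. Section 2.14 itself calls scarring rare, describes pigment change as reported to be transient, and says staining usually fades. These points limit how often the problem would arise, but they do not supply the missing criterion.

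A reader might further infer that the severity grade merely repeats the pain score. It does not. The 0 to 10 scale measures treatment discomfort and is scheduled only at treatment visits (2.12), whereas the grade covers every adverse event throughout the study and includes interference with activities.

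**Conclusion.** The gap is real and worth correcting. The single compulsory severity scale cannot separate a painless lasting skin change from a trivial transient one, and section 2.14 names four effects of that kind. The conclusion assumes that the event is painless and non-limiting and that the rater applies the wording as written.

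The consequence is conditional. Harm can be understated if results are shown by grade, or if the physician's judgement of acceptability relies on grade. The plan does not say whether either will happen. No number of affected subjects can be given, because the documents supply no incidence for these effects.

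**What to change.** 1. **Section 2.15.6.** Report adverse events by type, with outcome at last follow-up. On a separate line, give the number and percent of subjects, with an exact 95% confidence interval, who have scarring, pigment change or staining still present at Visit 7. Show the time since the treatment that preceded onset, and state how many treated subjects had no Visit 7 assessment.

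2. **Section 14.0.** Keep three grades. For visible skin events, add a criterion based on visible extent or disfigurement and on need for treatment to resolve. Where the existing and added criteria give different grades, the higher one counts. Record duration as its own item, and do not set the grade by status at Visit 7.

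The cost is a short protocol change, minor additions to the case report form and one extra table line. Adverse events and photographs are already collected at Visit 7, so no visit, procedure or subject is added. The downside is that some events will receive a less favourable grade.
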